9.3.3 Removal of Subjects from Treatment or Assessment

Subjects may withdraw their consent to participate in the study at any time without prejudice. The Investigator must withdraw from the study any subject who requests to be withdrawn. Such subjects will always be asked about the reason(s) for withdrawal. The Investigator will discuss with the subject appropriate procedures for withdrawal from the study. The Investigator should ask the subject's consent to perform the procedures listed under the early termination visit. Should a subject withdraw from the study, all efforts will be made to complete and report the observations as thoroughly as possible up to the date of the withdrawal.

A subject's participation in the study may be discontinued at any time at the discretion of BioMarin or of the Investigator and in accordance with his/her clinical judgment. When possible, the tests and evaluations listed for the termination visit should be carried out and every effort will be made to gather follow-up safety data if possible.

BioMarin must be notified of all subject withdrawals as soon as possible. BioMarin also reserves the right to discontinue the study at any time for either clinical or administrative reasons and to discontinue participation by an individual Investigator or site for poor enrollment or noncompliance.

Reasons for which the Investigator or BioMarin may withdraw a subject from the study include, but are not limited to, the following:

- Subject requires medication or medical procedure prohibited by the protocol
- Subject does not adhere to study requirements specified in the protocol
- Subject was erroneously enrolled into the study or does not meet entry criteria and not yet been dosed with BMN 270; subjects who do not meet entry criteria but who erroneously receive BMN 270 should remain in the study for safety monitoring
- Subject is lost to follow-up

If a subject fails to return for scheduled visits, a documented effort must be made to determine the reason. If the subject cannot be reached by telephone, a certified letter should

Page 61

be sent to the subject requesting contact with the Investigator. This information should be recorded in the study records.

The Investigator or designee must explain to each subject, before enrollment into the study, that for evaluation of study results, the subject's protected health information obtained during the study may be shared with the study Sponsor, regulatory agencies, and IRB/IEC/REB. It is the Investigator's (or designee's) responsibility to obtain written permission to use protected health information per country-specific regulations, such as the Health Insurance Portability and Accountability Act (HIPAA) in the US, from each subject. If permission to use protected health information is withdrawn, it is the Investigator's responsibility to obtain a written request, to ensure that no further data will be collected from the subject and the subject will be removed from the study.

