[name]		
NAME OF FINISHED PRODUCT:	Volume:	
BMN 270	Page:	
NAME OF ACTIVE INGREDIENT: AAV5-hFVIII-SO	Reference:	

- 21. Known allergy or hypersensitivity to BMN 270 investigational product formulation.
- 22. Unwilling to receive blood or blood products for treatment of an adverse event and/or a bleeding episode.

INVESTIGATIONAL PRODUCT(S), DOSE, ROUTE AND REGIMEN:

Each subject will receive a single intravenous infusion of BMN 270 at 6E13 vg/kg. The volume of infusion will depend on the subject's weight.

REFERENCE THERAPY(IES), DOSE, ROUTE AND REGIMEN:

No reference therapy will be evaluated in this study.

DURATION OF TREATMENT:

BMN 270 is given as a single dose by intravenous infusion.

CRITERIA FOR EVALUATION:

Efficacy:

Primary efficacy endpoint:

Change of the hFVIII activity, as measured by chromogenic substrate assay, during
Weeks 49-52 post-BMN 270 infusion from baseline. Each subject's hFVIII activity during
Weeks 49-52 is defined as the median of the values obtained during this 4-week window.
Values for hFVIII activity will be excluded if obtained within 72 hours since the last
infusion of exogenous FVIII protein concentrates.

Secondary efficacy endpoints:

- Change in the annualized utilization (IU/kg) of exogenous FVIII replacement therapy during Week 5 to Week 52 post-BMN 270 infusion from the baseline utilization of exogenous FVIII replacement therapy.
- Change in the annualized number of bleeding episodes requiring exogenous FVIII replacement treatment (annualized bleeding rate, ABR) during Week 5 to Week 52 of the study post-BMN 270 infusion from the baseline ABR.

Tertiary efficacy endpoints:

- Change from baseline in the total score of HAEMO-QoL-A at Week 52 of the study post-BMN 270 infusion.
- Change from baseline in the EQ-5D-5L score at Week 52 of the study post-BMN 270 infusion.
- Change from baseline in the Haemophilia Activities List (HAL) score at Week 52 of the study post-BMN 270 infusion.

Page 17

NAME OF COMPANY	SUMMARY TABLE	FOR NATIONAL
BioMarin Pharmaceutical Inc.	Referring to Part of the	AUTHORITY USE
[name]	Dossier:	ONLY:
[name]		
	Volume:	
NAME OF FINISHED PRODUCT:		
BMN 270	Page:	
NAME OF ACTIVE INGREDIENT:		
	Reference:	
AAV5-hFVIII-SQ		

- Change from baseline in the Work Productivity and Activity Impairment plus Classroom Impairment Questions: Hemophilia Specific (WPAI+CIQ:HS) score at Week 52 of the study post-BMN 270 infusion.

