9.4.8 Prior and Concomitant Medications

All prescription and over-the-counter medications (including dietary and herbal supplements) taken by a subject for 30 days before Screening will be recorded on the designated eCRF. The Investigator may prescribe additional medications, deemed necessary to provide adequate prophylactic or supportive care, during the study, as long as the prescribed medication is not prohibited by the protocol. In the event of an emergency, any needed medications may be prescribed without prior approval, but the Medical Monitor must be notified of the use of any contraindicated medications immediately thereafter. Any concomitant medications added or discontinued during the study should be recorded on the eCRF. Medications should, whenever possible, not be recorded in the electronic database with a frequency of PRN.

The following medications are prohibited starting 30 days before Screening and through the end of the study, and the Sponsor must be notified if a subject receives any of these during the study:

- Any investigational therapy
- Systemic immunosuppressive agents, except for corticosteroids
- Emicizumab
- Fitusiran
- Concizumab
- Efavirenz
- Lamivudine

Page 66

The following medications should be avoided, starting 30 days prior to and for at least 52 weeks after BMN 270 infusion and minimized throughout the remaining duration of the study.

- Alcohol
- Herbal and natural remedies and dietary supplements
- Medications which may be hepatotoxic

Vaccines should also be avoided during this period, but in particular during the first 26 weeks unless clinically indicated.

The following medications should be avoided during oral corticosteroid therapy:

- Vaccines
- NSAIDs

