14.8 Analysis Populations

The intention-to-treat (ITT) population is defined as all subjects who receive BMN 270 infusion, and the modified intention-to-treat (mITT) population is defined as subjects who receive BMN 270 infusion and are HIV-negative. The mITT population will be used for the primary efficacy analysis and ITT will be used for the supportive efficacy analysis. The ITT population will also be used for the safety analysis.

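### Section 9.3.3 lets dosed subjects be withdrawn from the study for needing a prohibited medication or for non-adherence, although after the single infusion there is no treatment left to stop

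*Protocol*

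**What the plan says.** All references are to Amendment 3.

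- Section 9.3.3 lists reasons for which the investigator or sponsor may withdraw a subject from the study, as distinct from treatment. The first two are "Subject requires medication or medical procedure prohibited by the protocol" and "Subject does not adhere to study requirements specified in the protocol". Neither mentions whether the subject has been dosed.
- The third reason, erroneous enrolment, does make that distinction. It applies only before dosing, and "subjects who do not meet entry criteria but who erroneously receive BMN 270 should remain in the study for safety monitoring".
- The same section gives the sponsor and the investigator a general discretion to end participation at any time and says that the listed reasons are not exhaustive. After such a discontinuation it asks for the termination-visit tests when possible and says that "every effort will be made to gather follow-up safety data if possible". It plans no later bleeding, FVIII-use or FVIII-activity data.
- Section 9.4.8: "The following medications are prohibited starting 30 days before Screening and through the end of the study". The list includes systemic immunosuppressants other than corticosteroids, emicizumab, fitusiran and concizumab. If one of them is taken, that section requires only that the sponsor be told.
- Synopsis: "BMN 270 is given as a single dose by intravenous infusion".
- Section 14.8 defines the analysis set for safety and supportive efficacy by infusion alone: "ITT) population is defined as all subjects who receive BMN 270 infusion". The primary efficacy set (mITT) is its HIV-negative part. Section 9.3.4 rules out replacing dosed subjects who withdraw.

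**The concern.** Withdrawal for a prohibited medication makes sense while there is a treatment to stop. Here there is none after Day 1. The vector cannot be taken back, and removing the subject only removes his data.

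The trigger may also depend on the result. It is a reasonable inference, though the protocol does not say so, that another haemophilia agent would be sought when bleeding persists, and a non-corticosteroid immunosuppressant when a liver reaction does not settle. Subjects who leave for such reasons would not be a random sample of those dosed.

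At stake are the completeness of a population defined by infusion, the Week 52 efficacy comparisons that rest on it, and the objective in Section 8 of assessing long-term safety.

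**Working it through.** **1. The list set against itself.** A dosed subject who should never have been enrolled is kept in for safety monitoring. A dosed, eligible subject who needs a prohibited agent, or who deviates, may be removed. The principle that dosing brings continued observation is recognised in one line of the list and missing from the two lines above it. No other section of the protocol restores it for these subjects.

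**2. Observation lost per subject.** Section 9.3.5 gives 4 weeks of screening + 52 weeks of post-infusion follow-up + 208 weeks of long-term follow-up = 264 weeks, of which 52 + 208 = 260 follow the infusion. A subject withdrawn at Week w loses 260 − w weeks. If w is 52 or less, that includes all 208 long-term weeks. Section 12.7.3 schedules 4 site visits in each of Years 2 to 5, so 4 × 4 = 16 such visits go with them.

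**3. How the missing values are filled.**

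| Endpoint | Rule (Sections 14.2, 14.3) | Effect if a failure exits |
|---|---|---|
| FVIII activity, Weeks 49-52 | Last 4-week window with a valid value | Favours BMN 270 only if that window precedes the decline |
| FVIII use | Change set to 0 | Works against BMN 270 |
| ABR | Median of the observed changes | Favours BMN 270 if the true change is worse than that median; applies only when no change value exists |

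**4. The plan's own power figure.** Section 14.7 takes SDs of 7.8 and 1.8 with zero correlation: √(7.8² + 1.8²) = √64.08 = 8.0, as stated. The effect size is 2.5/8 = 0.3125. With n = 110 and a 2-sided 0.05 one-sample t-test, the noncentrality is 0.3125 × √110 = 3.28 and the power is 0.901. The stated figure of about 90% is reproduced. It carries no allowance for withdrawal.

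**5. Power if subjects leave.** The protocol gives no withdrawal rate, so m below is an assumption. The same test on observed cases only (n = 110 − m) gives:

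- m = 5: 0.887
- m = 10: 0.872
- m = 15: 0.854

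The loss of power is modest. Bias is the larger issue.

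**6. Illustration of ABR bias.** Under the median rule the mean change moves in favour of BMN 270 by (m/110) × (true change − imputed median). Two further assumptions are needed: a true change of +5 bleeds per year in those who leave, and an imputed median between 0 and −2.5. The bracket is then 5 to 7.5.

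- m = 5: 0.23 to 0.34 bleeds per year
- m = 10: 0.45 to 0.68
- m = 15: 0.68 to 1.02

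These compare with a planned mean change of −2.5. They show the direction and how the shift scales. They are not estimates, because every input other than the 110 and the imputation rule is assumed.

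**The case against.** A reader might infer that treatment failures and toxicity cases in general turn into missing data. The protocol does not support that, for several reasons that stand:

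- Withdrawal is optional under 9.3.3, and 9.4.8 asks only for notification, which presupposes that the subject may continue.
- Subjects with recurrent bleeding may discuss resuming FVIII prophylaxis on study (9.8.3.1). Corticosteroids for raised ALT are exempt from the prohibition (9.4.8, 9.4.8.2).
- Subjects meeting the definition of treatment failure have an abbreviated Years 2-5 schedule (9.8.2.1, 12.7), so the sponsor intends to follow failures.
- Adverse events are followed to resolution, stabilization, explanation or loss to follow-up (10.6). Related deaths and serious events, and any cancer that comes to the investigator's attention, are notified after a subject leaves (10.7).
- Observed-case analyses are planned for the primary and secondary endpoints, and an MMRM for the primary.

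A reader might also attach a firm size to the bias. Assuming that 5% leave and that 20-40 IU/dL is carried forward in place of about 2 IU/dL gives 0.05 × 18 = 0.9 to 0.05 × 38 = 1.9 IU/dL, but none of those inputs is in the protocol. A subject who needs another agent because expression failed may already have a low value in his last window, and a shift of that order would not affect a test against zero. For ABR, a failure will usually have bled after Week 5 and may contribute an annualized rate, in which case the median rule does not apply. An error rate computed for that rule with data missing at random would describe the rule, not this withdrawal clause.

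None of this covers the subject who needs a listed agent, or who deviates, and is then withdrawn. The sensitivity analyses cannot recover outcomes that were never collected, and event follow-up under 10.6 and 10.7 is narrower than scheduled visits.

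**Conclusion.** The point holds for a defined subset: dosed subjects who need a prohibited medication or procedure, or who do not adhere, and whom the investigator or sponsor then chooses to withdraw. For them 9.3.3 permits an end to observation that serves no treatment purpose, contradicts the rule for ineligible dosed subjects, and may be related to outcome.

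The firm loss is up to 208 weeks of long-term follow-up per subject, against a stated long-term safety objective. The efficacy bias has a plausible direction for ABR, and for FVIII activity where the last window precedes a decline; the FVIII-use rule is conservative. Its size cannot be stated from the protocol. The link between exit and outcome is an inference from the prohibited list, not something the protocol reports.

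**What to change.** In Section 9.3.3:

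1. Limit the first two withdrawal reasons to subjects not yet dosed.
2. Add that, notwithstanding the general discretion of the sponsor and investigator in the same section, a dosed subject who starts a prohibited medication or deviates from the protocol stays in scheduled follow-up for safety, bleeding, FVIII use and FVIII activity, with the medication recorded as an intercurrent event, unless he withdraws consent or is lost to follow-up.

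The reference to the discretion clause is necessary. That clause is unrestricted and the list is not exhaustive, so editing the two reasons alone would leave the gap open. No change to which medications are prohibited, or to how any subject is treated, is proposed. The cost is a short amendment to one section and continued visits for a few subjects, which are already in the schedule.

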9.3.3.1 Study Safety Evaluation Criteria

If any of the following events occur in a subject in the study who has received BMN 270 infusion, an urgent evaluation by the DMC will be required and further enrollment into the trial will be temporarily put on hold if recommended by the DMC per Section 9.1.

- 1. Liver dysfunction (criteria do not apply to ALT elevations with an extra-hepatic etiology):
 - \circ ALT > 5x ULN, for more than 2 weeks
 - o ALT > 3x ULN and (total bilirubin > 2x ULN or INR > 1.5)
 - \circ ALT > 3x ULN with signs and symptoms of liver dysfunction
- 2. The occurrence of Grade 4 or Grade 5 adverse events assessed as related to study drug (events of liver dysfunction are defined above).
- 3. The occurrence of an AE of hepatic failure.
- 4. The detection of high-titer neutralizing antibodies (>5 BU) to hFVIII following BMN 270 infusion in two subjects.
- 5. The occurrence of any cancer (except non-melanoma skin cancer) at any point after BMN 270 infusion.
- 6. The occurrence of a thromboembolic event with FVIII activity > 150 IU/dL in one subject.

If any of the following events occurs in a subject in the study who has received BMN 270 infusion, an urgent evaluation by the DMC will be required. Further enrollment into the trial will continue while DMC evaluation is ongoing, unless deemed otherwise by the DMC:

1. The detection of high-titer neutralizing antibodies (>5 BU) to hFVIII following BMN 270 infusion in one subject.

Page 62

2. Occurrence of a thromboembolic event in one subject.

9.3.4 Subject Identification and Replacement of Subjects

Each subject will be assigned a unique subject identifier. This unique identifier will be on all eCRF pages. In legal jurisdictions where use of initials is not permitted, a substitute identifier will be used.

Subjects who withdraw from the study after receiving BMN 270 will not be replaced.

9.3.5 Duration of Subject Participation

The duration of participation for each subject will be approximately 264 weeks. This includes 4 weeks of screening, 1 day of BMN 270 infusion, 52 weeks of Post-Infusion Follow-Up, and 208 weeks of Long-Term Follow-Up.

9.4 Treatments

9.4.1 Treatments Administered

BioMarin and/or its designee will provide the study site with a supply of IP sufficient for the completion of the study. BioMarin is responsible for shipping study drug to clinical sites.

9.4.2 Identity of Investigational Product

9.4.2.1 Product Characteristics and Labeling

BMN 270 is a sterile, clear, colorless-to-pale yellow solution for IV infusion and is supplied in a 10 mL Crystal Zenith[®] (CZ) vial. Each vial contains 8.5 mL (extractable volume 8 mL) of AAV5-hFVIII-SQ at a concentration of 2E13 vector genomes per mL in a pH 7.4 phosphate buffer.

The study drug is labelled according to the particulars approved by the relevant regulatory agencies.

9.4.3 Storage

At the study site, all IP must be stored under the conditions specified in the Pharmacy Manual in a secure area accessible only to the designated pharmacists and clinical site personnel. All IP must be stored and inventoried and the inventories must be carefully and accurately documented according to applicable state, federal and local regulations, ICH GCP, and study procedures.

Page 63

9.4.4 Directions for Administration

On the day of infusion, the subject will come to the infusion site, where a physical examination will be performed by the Investigator or designee. If the subject is found to have an active acute illness at the time of planned infusion, then the infusion should be deferred until the illness has resolved; screening procedures may require repetition if outside the specified window. An IV catheter or butterfly needle will be inserted into a suitable peripheral vein (eg, the median cubital vein) and flushed with saline. FVIII replacement therapy will not be given since venipuncture is a minimally invasive procedure in these individuals under ordinary conditions.

BMN 270 will be prepared and infused as a pure solution over a dose-dependent time. Prepared drug will be kept at room temperature prior to administration. An electric syringe pump will be used to infuse through an in-line, low protein binding 0.22 micron filter. BMN 270 will be infused through the catheter using an appropriate infusion pump at an initial rate of 1 mL/min. The infusion rate should be increased every 30 minutes by 1 mL/min up to a maximum of 4 mL/min, provided that the subject's clinical condition permits such an increase. Of note, the IP has been shown to be stable at room temperature for 7.5 hours following completion of product thaw. Vital signs (pulse, blood pressure, respiration rate and temperature) should be monitored at 15 minute (±5 minutes) intervals throughout the time period of the infusion.

As with any infused biological product, there is a potential risk of acute, systemic hypersensitivity reactions (including anaphylaxis) with BMN 270. Dosing will be administered at a qualified infusion site, with appropriate resuscitation equipment and medication available and easily accessible.

Clinical staff administering BMN 270 should be trained appropriately in recognizing and managing the signs and symptoms associated with potential hypersensitivity, anaphylactic, and anaphylactoid reactions. Additionally, the Investigator should be familiar with Sampson's criteria for defining anaphylaxis (Sampson, 2006; Appendix 1).

Should symptoms of potential hypersensitivity occur, the infusion may be slowed or halted at the Investigator's discretion, with consideration of the subject's clinical condition. If the infusion is halted, it should only be restarted if the Investigator considers it safe and appropriate to do so. Antihistamines, anti-pyretic, and/or corticosteroid administration is permitted prior to restarting an interrupted infusion by an infusion-related reaction. At the restart, the infusion rate may be adjusted (ie, to a slower rate [minimum of 1 mL/min], with

Page 64

the rate increased every 30 minutes by 1 mL/min up to a maximum rate of 4 mL/min, if the subject's clinical condition permits such an increase) with careful monitoring of the subject.

In case of hypersensitivity or adverse drug reaction, safety assessment, including physical examination and vital signs, will be done and additional blood samples will be collected within 1 hour of the hypersensitivity reaction (eg, tryptase, C3, C3a, C4, C5, C5a, and cytokine bead array, as well as possible additional exploratory testing) and samples for IgE and cytokine bead array (and possible additional exploratory testing) between 8-24 hours after the reaction, if possible. In addition, a blood sample should be taken 1 week after the hypersensitivity reaction for assessment of the cytokine bead array. In-patient observation can be extended and additional blood samples can be collected if deemed necessary at the discretion of the Investigator and Medical Monitor.

Following completion of the infusion, vital signs will be monitored hourly (\pm 5 minutes). If the vital signs are stable the catheter will be removed 8 hours after the infusion. Hemostasis at the puncture site will be established by applying pressure according to standard protocol for infusing FVIII concentrates. Subjects will remain in the clinic for at least 8 hours to observe for any immediate toxicity of the procedure; in-patient observation can be extended beyond 8 hours if needed per Investigator discretion, or the subject may transfer to a separate facility based on the evaluation and judgment of the Principal Investigator after consultation with the Medical Monitor.

Prior to discharging subjects from the clinic, the Investigator or designee should instruct subjects how to recognize signs and symptoms of potential (delayed) hypersensitivity reactions and anaphylaxis, and to contact a medical practitioner or seek emergency care in case of such an event.

